**AST or ALT**

Grade 1 (> ULN - 2.5 x ULN)	Maintain dose level
Grade 2 (> 2.5 - 5.0 x ULN)	Maintain dose level
Grade 3 (> 5.0 and ≤ 8x ULN)	For ALT or AST > 5x ULN and ≤ 8x ULN: 
 
• Study medication should be temporarily interrupted & liver chemistry monitored every 3-4days until resolution or return to baseline.
 
• If resolution or return to baseline does not occur after 2 weeks, the patient should be discontinued.
 
• If ALT or AST returns to less than 5x ULN, study drug can be resumed and patient can continue study per protocol
 
• If ALT or AST rises above 5x ULN anytime after study drug is resumed, then study drug should be discontinued immediately.
 

Grade 4 (> 20.0 x ULN)	Omit dose and discontinue patient from study treatment

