## 6.6 Pasireotide LAR / placebo dose adjustment

As already described above, pasireotide LAR/placebo at 60 mg every 28 days is the recommended starting dose for oncological indications (including NETs). If tolerability issues occur, the treatment dose may be reduced to pasireotide LAR at 40 mg with next scheduled injection. Patients requiring a dose reduction can return to the higher dose once the tolerability issue is resolved. However, patients not able to tolerate the minimum pasireotide LAR dose of 20 mg are recommended to be discontinued from study.

All dose changes must be recorded on the Dosage Administration Record CRF. Table 7 outlines the dose reduction steps for pasireotide.

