**Table 7 Guideline for treatment of patients experiencing adverse events**

Recommended dose modifications for pasireotide/ placebo	
Worst toxicity CTCAE Grade* (value)	Recommended dose modification any time during a cycle of therapy
No toxicity	Maintain dose level
Hematologic	
Neutropenia (ANC)	
Grade 1 (ANC < LLN - 1500/mm  )	Maintain dose level
Grade 2 (ANC < 1500 - 1000/mm  )	Maintain dose level
Grade 3 (ANC < 1000 - 500/mm  )	Omit dose until resolved to ≤ Grade 2, then ↓ 1 dose level 
 
• If resolved ≤ 7 days, then maintain dose level
 
• If resolved > 7 days, then ↓ 1 dose level
 

Grade 4 (ANC < 500/mm  )	Omit dose until resolved to ≤ Grade 2, then ↓ 1 dose level 
 
• If resolved ≤ 7 days, then maintain dose level
 
• If resolved > 7 days, then ↓ 1 dose level
 

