**Renal****Serum creatinine**

< 2 x ULN	Maintain dose level
2-3 x ULN	Omit dose until resolved to ≤ Grade 1, then 
 
• If resolved ≤ 7 days, then maintain dose level
 
• If resolved > 7 days, then ↓ 1 dose level
 

Grade 3 (> 3.0 - 6.0 x ULN)	Omit dose and discontinue patient from study treatment
Grade 4 (> 6.0 x ULN)	Omit dose and discontinue patient from study treatment

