**Hepatic See also section 7.5.4.1****Bilirubin**

Grade 1 (< 2 x baseline value)	Maintain dose level
Grade 2 (2-3 x baseline value)	Omit dose until resolved to ≤ Grade 1, then 
 
• If resolved ≤ 7 days, then maintain dose level
 
• If resolved > 7 days, then ↓ 1 dose level
 

Grade 3 (> 3.0 - 10.0 x ULN)	Omit dose until resolved to ≤ Grade 1, then 
 
• If resolved ≤ 7 days, then maintain dose level
 
• If resolved > 7 days, then ↓ 1 dose level
 

Grade 4 (> 10.0 x ULN)	Omit dose and discontinue patient from study treatment

NOTE: If grade 3 or 4 hyperbilirubinemia is due to the indirect (unconjugated) component only, and hemolysis as the etiology has been ruled out as per institutional guidelines (e.g. review of peripheral blood smear and haptoglobin determination), then ↓ 1 dose level and continue treatment at the discretion of the investigator

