## 6.8 Study drug discontinuation

Study drug must be discontinued and the subject withdrawn from the trial if the investigator determines that continuing would result in significant safety risk for that subject. The following circumstances require study drug discontinuation:

Pregnancy

The occurrence of an adverse event or of a clinically significant laboratory change or abnormality that, in the judgment of the investigator, warrants discontinuation of treatment.

Subjects who have fasting plasma glucose > 240 mg/dL confirmed by repeat measurement

Any CTC grade 3 or higher abnormalities in hematology or chemistry parameters judged clinically significant by the Investigator

Any confirmed QTcF > 500 ms or confirmed increase of QTcF > 60 ms from baseline

ALT or AST > 3x ULN and Total Bilirubin  $\geq$  2 x ULN and ALP > 2 x ULN

ALT or AST > 5x ULN and  $\leq$  8 x ULN persistent for more than 2 weeks

ALT or AST > 8 x ULN

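### Table 7 gives no action for AST or ALT above 8 and up to 20x ULN and prints its only unconditional stop at > 20x ULN, while 6.8, 7.5.4.1 and Appendix 4 stop at > 8x ULN

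*Combined protocol and SAP*

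**What the plan says.** Section 6.6 sends the reader to the table for dosing decisions: "Table 7 outlines the dose reduction steps for pasireotide". The table is headed "Recommended dose modifications for pasireotide/ placebo".

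Its AST/ALT series has four rows. The first two, up to 2.5x ULN and up to 5x ULN, maintain the dose. The third, "Grade 3 (> 5.0 and ≤ 8x ULN", interrupts treatment and repeats liver chemistry every 3 to 4 days. It has two conditional stops: no resolution after 2 weeks, or a new rise above 5x ULN after treatment is resumed. The fourth, "Grade 4 (> 20.0 x ULN", omits the dose and discontinues the patient.

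Three other places set the stop at > 8x ULN:

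- Section 6.8 lists it under the sentence "The following circumstances require study drug discontinuation".
- Section 7.5.4.1 lists it among the criteria for immediate discontinuation and prohibits re-challenge once a criterion is met.
- Appendix 4 (12.4) repeats the list and the prohibition.

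The heading of the hepatic block in Table 7 reads "Hepatic See also section 7.5.4.1".

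**The concern.** Someone who looks up an ALT of 12x ULN in Table 7 finds no instruction, and the first unconditional stop they see is at > 20x. The Grade 3 row follows the part of 7.5.4.1 that covers > 5x to 8x, but the > 8x stop that comes after it in 7.5.4.1 has no row.

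The table is likely to be consulted when a dose is due. Day 22 and Day 50 liver tests must be assessed before the Day 29 and Day 57 injections (Table 8, footnote 4). The product is a depot: section 1.5.1.1.1 describes slow release for up to 42 days after one injection in healthy volunteers, so a dose given in error cannot be taken back. A plausible misreading is to treat 12x ULN as not yet Grade 4, apply the Grade 3 row, and resume once the value falls below 5x. Section 7.5.4.1 and Appendix 4 forbid that.

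**Working it through.** The plan gives no figure to reproduce here. The check compares thresholds.

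**Step 1: coverage of the AST/ALT rows.** In multiples of ULN, the Table 7 bands are above 1 to 2.5, above 2.5 to 5, above 5 to 8, and above 20. The uncovered interval is above 8 to 20, a width of 20 − 8 = 12x ULN. The ratio of the printed stop to the required stop is 20 / 8 = 2.5.

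**Step 2: sample values against each rule.**

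| ALT or AST (x ULN) | Table 7 | 6.8, 7.5.4.1 and Appendix 4 |
|---|---|---|
| 6 | Interrupt and monitor; conditional stops | 7.5.4.1: the same; all three stop if > 5x to 8x lasts more than 2 weeks |
| 8.1 | No row | Discontinue |
| 12 | No row | Discontinue |
| 20 | No row | Discontinue |
| 20.1 | Discontinue | Discontinue |

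No value receives opposite instructions. The fault is an absent action between 8x and 20x, together with a printed stop that is not the protocol's stop.

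**Step 3: is a jump between Grade 3 and Grade 4 normal for this table?** The table has seven graded laboratory series.

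| Series | Grade 3 ends | Grade 4 starts |
|---|---|---|
| ANC (/mm³) | 500 | 500 |
| Platelets (/mm³) | 25,000 | 25,000 |
| Creatinine (x ULN) | 6.0 | 6.0 |
| Bilirubin (x ULN) | 10.0 | 10.0 |
| AST/ALT (x ULN) | 8 | 20.0 |
| Amylase/lipase (x ULN) | 5.0 | 5.0 |
| Glucose (mg/dL) | 500 | 500 |

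One of seven has a gap at this boundary. Creatinine ("Grade 4 (> 6.0 x ULN") and bilirubin ("Grade 4 (> 10.0 x ULN") show the usual pattern, in which Grade 4 begins where Grade 3 ends. The glucose rows only refer to Appendix 2 for action, so that series adds little to the comparison.

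**Step 4: limit of Step 3.** The comparison covers the Grade 3 to Grade 4 boundary only. For bilirubin, Grade 2 ends at 3x the patient's baseline, while Grade 3 starts above 3.0x ULN. With baseline b in multiples of ULN, Grade 2 ends at 3b x ULN, so any b below 1 leaves a gap from 3b to 3.0x ULN. For an assumed b of 0.5, which is within the eligibility limit of 1.5x ULN, the gap runs from 1.5x to 3.0x ULN. AST/ALT is therefore not the only series in the table with an uncovered range.

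**Step 5: could this be a text-extraction fault?** It is unlikely. The Grade 3 action cell repeats the > 5x to 8x range in its own text, so the upper limit of 8x does not depend on the row label alone.

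**The case against.** The strongest defence is that the governing rule is present and outranks the table. Table 7 is a guideline of recommended modifications, while 6.8 is worded as a requirement. Section 6.8 also stops treatment for any Grade 3 or higher chemistry abnormality that the investigator judges clinically significant. The hepatic heading refers to 7.5.4.1, and that section is hard to avoid in practice: it calls for a work-up within 72 hours of awareness of abnormal liver tests and repeat chemistry every 3 to 4 days. Anyone managing an ALT above 8x should already have the page with the > 8x stop open. Stopping above 20x is also a subset of stopping above 8x, so the two rules do not conflict for any value.

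All of this stands, and it rules out two stronger readings. A reader might infer that the protocol allows dosing up to 20x ULN. It does not: the table says nothing between 8x and 20x, and three sections require or direct a stop. A reader might also infer that AST/ALT is the one faulty series in an otherwise continuous table. The bilirubin change of units shows otherwise.

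The defence does not make the row correct. A cross-reference is no reason for the dosing table to print a different stop from the section it refers to.

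Section 1.5.2.1 also cites a Table 7 for added liver discontinuation criteria. No weight is placed on that, because its citations of Tables 1 and 2 do not match this protocol's tables of those numbers.

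**Conclusion.** The point holds as a minor safety-consistency correction. The AST/ALT rows give no action over a range 12x ULN wide, and their only unconditional stop is 2.5 times the protocol's own threshold. The > 8x stop appears in three sections and in no row of Table 7. The requirement is literal in 6.8; 7.5.4.1 and Appendix 4 use directive wording (should be discontinued immediately) and add the re-challenge ban.

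The practical risk is limited to staff who use the table without 6.8, 7.5.4.1 or Appendix 4. The documents do not allow an estimate of how many patients would have values in the gap. Nothing here bears on the liver-volume endpoint, the sample size or the power. The conclusion assumes only that the > 8x rule, stated consistently in three places, is the intended one.

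**What to change.** In Table 7, replace the AST/ALT row for > 20x ULN with: > 8x ULN, discontinue immediately, no re-challenge. Any value above 20x is also above 8x, so nothing is lost, and the new row joins the end of the Grade 3 row without a gap.

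The cost is the wording of one table row, handled by the amendment route in section 9. No rule, test or visit is added, because the change only brings the table into line with 6.8, 7.5.4.1 and Appendix 4.

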**Pancreatic****Pancreatitis**

Grade 1	Maintain dose level
---------	---------------------

Grade 2	Maintain dose level
Grade 3	Omit dose and discontinue patient from study treatment
Grade 4	Omit dose and discontinue patient from study treatment
Amylase and/or lipase	
Grade 1 (> ULN - 1.5 x ULN)	Maintain dose level
Grade 2 (> 1.5 - 2.0 x ULN)	Maintain dose level
Grade 3 (> 2.0 - 5.0 x ULN)	For asymptomatic: Omit dose until resolved to ≤ Grade 1, then 
 
• If resolved ≤ 7 days, then maintain dose level
 
• If resolved > 7 days, then ↓ 1 dose level
 
 For symptomatic: Omit dose and discontinue patient from study treatment
Grade 4 (> 5.0 x ULN)	Omit dose and discontinue patient from study treatment A CT scan or other imaging study to assess the pancreas, liver and gallbladder must be performed within 1 week of the first occurrence of any ≥ CTCAE grade 3 of amylase and/or lipase.
Endocrine/metabolic	
Fasting plasma glucose (FPG) or 2-hour postprandial capillary glucose (PPG)	
FPG <126 mg/dL or PPG < 140 mg/dL	Maintain dose level
Grade 1 (> ULN – 160 mg/dL)	appendix 2 section 12.2.
Grade 2 (> 160 – 250 mg/dL)	appendix 2 section 12.2.
Grade 3 (> 250 – 500 mg/dL)	appendix 2 section 12.2.
Grade 4 (> 500 mg/dL)	appendix 2 section 12.2.
Cardiac	
Cardiac - prolonged QTc interval	

 
• QTcF > 480 ms and ≤ 500 ms
 
• QTcF > 500 msec
 
	
If at any time a QTcF > 480 ms and ≤ 500 ms is observed a cardiology consultation must be sought to re-evaluate the abnormal ECG finding.
 
 
1. Triplicate ECGs (2-3 minutes apart) need to be taken approximately 1 hour after the initial ECG.
 
2. If the mean QTcF is > 500 ms, the patient must postpone study treatment until a cardiologist has re-evaluated the ECG.
 
3. The re-evaluation of ECG needs to be done as soon as practical but within 7 days of the initial abnormal ECG.
 
4. If the cardiologist confirms a mean QTcF > 500 ms, the patient must be discontinued.
 

Cardiac general	
Grade 1 or 2	Maintain dose level
Grade 3	Omit dose until resolved to ≤ Grade 1, then ↓ 1 dose level
Grade 4	Omit dose and discontinue patient from study treatment
Other adverse events	
Grade 1 or 2	Maintain dose level
Grade 3	Omit dose until resolved to ≤ Grade 1, then ↓ 1 dose level
Grade 4	Omit dose and discontinue patient from study treatment
Detailed treatment guidance on QT prolongation, hyperglycemia and diarrhea will be provided as appendices of the protocol	

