## **7 Visit schedule and assessments**

Table 8 lists all of the assessments and indicates the visits at which they are to be performed with an "X". All data obtained from these assessments must be supported in the patient's source documentation. In year 2, safety assessments for patient's crossing over from placebo to SOM 230 will be required. These will be per the same schedule after the first SOM230 injection as was performed in year 1 for all patients enrolled.

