 Height required only at pre-study 12 lead ECG & interpretation at screening and ½ hour after first injection. Repeat ECG on 21st day after injection for the first 3 months then every third month. All ECGs are faxed to the Mayo Clinic ECG Core lab. Includes WBC with differential Comprehensive fasting metabolic panel includes: albumin, total bilirubin, calcium, CO2, (bicarbonate) chloride, creatinine, BUN, potassium, total protein, sodium, AST, ALT, ALP,, and glucose. Liver function tests are assessed at baseline (if baseline LFTs are **done within 7 days of day 1 of treatment** they do not have to be repeated on day 1), day 22 after first injection, day 29, day 50, 57 and 85. After day 85 and the 4th LAR Injection, monitoring should follow the existing protocol schedule. Day 22 & 50 LFTs must be available & assessed prior to dosing on days 29 (2nd injection) and 57 (3rd injection). Only in patients with associated PKD. Hemoglobin A1C is done at baseline and 3 monthly Thyroid function is also acceptable if checked within 30 days of the screening visit Bi-weekly cyclosporin levels will be monitored for the first month in enrolled patients who are on this medication (mail in test) Plasma glucose is required 6 hours after first injection. Monitor FPG or finger stick at baseline and at 21st day of treatment for first 3 months. Monitor FPG or finger stick monthly (or as clinically appropriate), thereafter.

-  Women of childbearing potential only (urine pregnancy test). If CT scan is needed, a negative pregnancy result will need to be obtained prior to performing the CT. For women of child bearing potential who will be having an MRI – a pregnancy test is not required at month 12.
-  SOM230/placebo IM injections will be given every 28 days, +/- 2 days.
-  No gallstone assessment is needed on visits where MRI is performed, as gallstones will be detected on MRI if present.
-  In year 2, safety assessments for patients crossing over from placebo to SOM 230 will be required. These will be per the same schedule after the first SOM230 injection as was performed in year 1 for all patients enrolled.

At a minimum the following safety evaluations (Table 9) are to be included in all protocols.

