## **7.5 Safety**

Safety assessments will consist of monitoring and recording all adverse events, including serious adverse events, the regular monitoring of hematology (including glycosylated hemoglobin and coagulation parameters), blood chemistry (including fasting glucose, thyroid function tests), urine for microalbumin, regular monitoring of vital signs, gallbladder by MRI/CT ultrasound, will be recorded from study enrollment until study completion.

Patients with diabetes are to be instructed to check blood glucose levels via a fingerstick several times daily, particularly for the first few days of treatment.

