### **7.5.4 Laboratory evaluations**

Patients are to fast overnight for 8 hours prior to all biochemistry samples being taken. Blood samples are to be taken in the morning. Water is allowed during this time. Laboratory samples will be analyzed locally at Mayo Clinic. Albumin, alkaline phosphatase, total bilirubin, calcium, chloride, creatinine with calculated eGFR,  $\gamma$ -GT, fasting blood glucose, potassium, total protein, AST, ALT, sodium, urea/BUN. If the total bilirubin concentration is increased above 1.5 times the upper normal limit (UNL), total bilirubin should be differentiated into the direct and indirect reacting bilirubin.

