#### **7.5.4.1 Abnormal liver function management:**

Perform within 72 hours of awareness of abnormal LFTs:

Perform liver-directed medical history and physical examination (i.e. assess occupational hazards, concomitant medications including OTC meds, intercurrent illness, etc)

Liver chemistry tests: ALT, AST, total bilirubin, (fractionate to direct/indirect bilirubin if total bilirubin is > 2.0x ULN), Alb, PT (INR), ALP, and GGT

Perform hepatitis screen: anti-HAV, IgM (to confirm acute hepatitis A), HbsAg, Anti-HBc, anti-HCV (if positive PCR viral load should be assessed), Anti-HEV, ANA antibodies, anti-smooth muscle anti-bodies, CMV, EBV

Perform abdominal ultrasound (liver and biliary tree)

Liver chemistry tests should be monitored every 3-4 days for LAR studies until resolution or return to baseline status.

For ALT or AST > 5x ULN and ≤ 8x ULN:

- Study medication should be temporarily interrupted and liver chemistry tests monitored **every 3-4 days** until resolution or return to baseline
- If resolution or return to baseline does not occur after 2 weeks, the patient should be discontinued.
- If ALT or AST returns to less than 5x ULN, study drug can be resumed and patient can continue study per protocol
- If ALT or AST rises above 5x ULN anytime after study drug is resumed, then study drug should be discontinued immediately.

Resolution return to baseline does not occur after two weeks the patient should be discontinued

If ALT or AST rises about 5X ULN anytime after study drugs resumed and study drug to be discontinued immediately

Study medication should be discontinued immediately if any of the discontinuation criteria below are met: (see appendix 4)

ALT or AST > 3x ULN and Total Bilirubin ≥ 2x ULN and ALP < 2x ULN

ALT or AST > 5x ULN and ≤ 8x ULN persistent for more than 2 weeks

ALT or AST > 8x ULN

Re-challenge of study medication is prohibited once discontinuation criteria are met.

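### Table 7 acts on grade 3 or higher amylase or lipase, but neither enzyme is scheduled on treatment, so silent elevations would be found only by off-schedule testing

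*Combined protocol and SAP*

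**What the plan says.** Table 7 in section 6.6 has a row for amylase and/or lipase. Grade 3 (above 2.0 and up to 5.0 x ULN) is split. Without symptoms the dose is omitted until the value is back to grade 1 or lower; with symptoms the patient stops study treatment. Grade 4 (above 5.0 x ULN) means stopping in either case. The column is headed "Recommended dose modification any time during a cycle of therapy", so the dose actions are recommendations. The imaging instruction is firmer: a CT or other study of the pancreas, liver and gallbladder "must be performed within 1 week of the first occurrence of any ≥ CTCAE grade 3 of amylase and/or lipase".

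Section 6.8 adds, among the circumstances that require discontinuation, "Any CTC grade 3 or higher abnormalities in hematology or chemistry parameters judged clinically significant by the Investigator".

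On when tests are done, section 7 states that "Table 8 lists all of the assessments and indicates the visits at which they are to be performed". Footnote 4 to Table 8 itemises the metabolic panel, ending with "creatinine, BUN, potassium, total protein, sodium, AST, ALT, ALP,, and glucose". Section 7.5 describes "blood chemistry (including fasting glucose, thyroid function tests" in open-ended terms. Section 7.5.4 gives its own list, which starts "Albumin, alkaline phosphatase, total bilirubin, calcium, chloride, creatinine with calculated eGFR". The work-up for abnormal liver tests in 7.5.4.1 closes with "Alb, PT (INR), ALP, and GGT". None of these names amylase or lipase.

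The enzymes appear as a test requirement only in section 5.2.1, where both must be at or below 1.5 x ULN for entry. Even that screening test is missing from Table 8.

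**The concern.** Symptoms cannot trigger a branch written for patients without symptoms; only a measurement can, and the plan schedules none. Unless someone orders the test off schedule, a patient with a silent grade 3 or 4 value continues monthly injections without the recommended hold or discontinuation and without the mandatory imaging. The section 6.8 criterion is equally inactive for these two enzymes.

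Symptoms are also a weak prompt in this population. Section 1.1 lists abdominal pain as a feature of polycystic liver disease, and section 1.5.1 lists it among the most frequent adverse events on pasireotide.

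This is a patient-safety matter. It is a gap in monitoring, not a contradiction: the clinical Pancreatitis row of Table 7 and symptom-driven testing still work.

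**Working it through.** **1. Rules against schedule.** No arithmetic applies here; the sections are set side by side.

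| Place | Amylase or lipase listed? |
|---|---|
| 5.2.1 entry criterion | Yes, at or below 1.5 x ULN |
| Table 7, Pancreatic | Yes, as action triggers |
| Table 8 rows | No |
| Table 8 footnote 4 (panel contents) | No |
| Table 9 (core safety evaluations) | No |
| 7.5 Safety | No |
| 7.5.4 laboratory list | No |
| 7.5.4.1 abnormal liver-test work-up | No |

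The finding does not rest on Table 8 alone, because that table is not fully complete: urinalysis has no row. But section 7.5.4.5 does say that urinalysis will be assessed. No section says this of amylase or lipase on treatment.

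The other laboratory and ECG rows of Table 7 have a scheduled source: creatinine, bilirubin and AST/ALT in the metabolic panel, neutrophils and platelets in the heme group (reading that label in its ordinary sense), fasting glucose and QTcF in their own rows.

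**2. Coverage in year 1.** Table 8 marks the metabolic panel at days 22, 29, 50, 57 and 85 and at months 6, 9 and 12. That is 5 + 3 = 8 post-dose panels, and 0 of 8 contain either enzyme.

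**3. Spacing of the panels.** Month 6 is about 365.25/2 = 183 days, so the gap after day 85 is 183 − 85 = 98 days. With injections on days 1 + 28k, those inside the gap fall on days 113, 141 and 169, three in all. Adding the enzymes to existing panels leaves this gap, so a transient rise between draws can still be missed.

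**4. Distance from entry limit to action limit.** A patient entering at 1.5 x ULN passes the grade 3 limit of 2.0 x ULN after a rise of one third (2.0/1.5 = 1.33).

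**5. Assays needed for the fix.**
- Screening plus 8 year-1 panels: 2 enzymes x 9 draws x 48 patients = 864.
- Repeated early visits after crossover: at most 2 x 5 x 16 = 160.
- Total: 864 + 160 = 1,024. Screen failures and the later year 2–3 panels are not counted.

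**6. Power if more patients are discontinued.** Section 10.2 plans for 15 placebo and 30 SOM230 patients with endpoint data and names one standard deviation as the detectable difference for any quantitative endpoint. For a two-sided two-sample t-test at 0.05, the noncentrality is d·√(n₁n₂/(n₁+n₂)) with n₁+n₂−2 degrees of freedom, and d = 1.

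| Placebo vs SOM230 | Noncentrality | Power |
|---|---|---|
| 15 vs 30 | √(450/45) = 3.162 | 87.1% |
| 15 vs 29 | √(435/44) = 3.144 | 86.7% |
| 15 vs 28 | √(420/43) = 3.125 | 86.2% |

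The loss is (87.1 − 86.2)/2, or a little under half a point, per SOM230 patient lost beyond the dropout allowance of 2 SOM230 and 1 placebo.

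**The case against.** The best case against is that Table 7 is guidance on what to do once an abnormality is found, and its dose changes are recommendations. Such a rule does not promise surveillance, and the asymptomatic branch can still apply when the enzymes are ordered for another reason. The schedule is also incomplete elsewhere. Serum magnesium (an exclusion criterion and a QT-related discontinuation criterion) and the hepatitis serology have no line in Table 8 either, and the chemistry wording in 7.5 is open-ended. A clerical omission is therefore at least as plausible as a decision not to monitor.

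The evidence of harm is thin. Section 1.5.2.1 reports transient, resolved, symptom-free rises in liver tests and/or pancreatic enzymes in three volunteers, without grades. The account of the 85-patient LAR study in section 1.5.1.1 names no amylase, lipase or pancreatitis event. Pancreatitis and known gallbladder or bile duct disease are excluded at entry, and the gallbladder is imaged every 6 months.

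Routine testing also has a cost beyond assays. An asymptomatic grade 4 value would lead to discontinuation, and section 6.8 couples required discontinuation with withdrawal from the trial. Patients without a 12-month MRI leave the primary volume analysis and count as non-responders. If enzyme rises are drug-related, such losses would differ between arms.

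Much of this stands as a limit on size. The event rate is unknown, and the possible imbalance in losses is real and not priced here. But it does not close the gap. A clerical cause needs the same correction, and a site following the written plan still would not test. The exclusions and gallbladder imaging lower risk without detecting an enzyme rise. The added discontinuations would follow from the sponsor's own rule.

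**Conclusion.** The concern holds and should be fixed. The plan sets hold, stop and imaging rules for grade 3 or higher amylase or lipase and schedules no on-treatment measurement that could trigger them (0 of 8 year-1 panels). Confidence in this textual gap is high.

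The clinical consequence cannot be sized: the documents give no rate of grade 3 or higher elevation, show none on this drug, and none is assumed. The conclusion assumes that sites test what the protocol lists and no more; off-schedule testing would narrow the gap. It also assumes that the heme group includes platelets, which matters only for the comparison with the other Table 7 rows.

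**What to change.** Add amylase and lipase to footnote 4 of Table 8 and to the list in section 7.5.4, at screening and at every metabolic-panel visit already scheduled, including the early visits repeated for patients crossing over from placebo. Leave the entry limit in 5.2.1 and the limits and actions in Table 7 and section 6.8 as they are. Requiring the day 22 and day 50 enzyme results before the next injection is optional; section 1.5.2.1 sets that rule for liver tests only.

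No new visit or blood draw is needed. The cost is the 1,024 assays derived above, run wherever the liver-test sample is analysed (section 4 places some safety testing at sub-sites), plus the extra holds, imaging and discontinuations that Table 7 already calls for.

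If the sponsor does not want routine enzyme testing, the alternative is to state in Table 7 that the row applies only to clinically prompted tests.
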